2. STUDY DESIGN

Overview: We propose a randomized two-arm parallel group trial to determine if lactulose therapy in cirrhosis patients with portal hypertension who report moderate to high regular daily activity impairment and have no history of prior lactulose use or HE within 6 months, improves their HRQOL, cognitive function and overall sleep quality at 28 days post-baseline. Subjects will be randomized to one of two groups:

- 1) Treatment: subjects prescribed and instructed to take 20g (dissolved in 4oz of water) dose of lactulose twice daily (upon awakening and then 4 hours later) for 28 days.
- 2) Control: subjects are asked to complete baseline and outcome assessments at 28 days and no intervention or placebo will be prescribed.

Our goal is to have 50 patients with cirrhosis who meet study eligibility criteria (see Section 3 below) complete study participation, with approximately 25 subjects in each arm. We will enroll up to 75 subjects to account for subject withdrawals, lost to follow-up, death, transplant or PI discretion.

Figure 1. Study Design

We will enroll patients with cirrhosis who report impairment of daily activities, defined by scores ≥ 3 on the 0-10 activity impairment scale from the Work-Productivity Activity index and assess the impact of lactulose therapy on health-related quality of life (HRQOL), cognitive function (animal naming test, ANT), sleep quality, and falls

3. SELECTION AND ENROLLMENT OF SUBJECTS

3.1 INCLUSION CRITERIA

All subjects must meet the following criteria:

1. *Adult ≥ 18 years of age*
2. *Diagnosis of cirrhosis – must meet one of the following criteria:*
 - a. *liver biopsy, OR*
 - b. *history of cirrhosis complication: ascites, variceal bleeding, hepatic encephalopathy, OR*
 - c. *2 of the following 4 criteria:*
 1. *US, CT or MRI imaging findings of cirrhosis (cirrhotic appearing liver, splenomegaly, varices, ascites)*
 2. *Fibroscan liver stiffness score >13 kPa*
 3. *Laboratory testing: AST/platelet ratio index (APRI) >2.0*
 4. *CT, MRI or EGD showing presence of esophageal varices*
3. *Evidence of portal hypertension – must meet at least one of the following criteria:*
 - a. *Ascites*
 - b. *Varices (seen by endoscopy or by ultrasound or cross-sectional imaging)*
 - c. *Fibroscan liver stiffness measurement (LSM) > 25*
 - d. *Platelets < 80*
4. *Moderate activity impairment*
 - a. *≥ 3 on WPAI regular daily activity impairment question (scored 0-10)*

3.2 EXCLUSION CRITERIA

The following exclusion criteria applies to all subjects:

1. *Non-English speaking*
2. *Unable or unwilling to provide consent*

- 3. *History of liver transplant*
- 4. *Disorientation at the time of enrollment, Dementia, or Treated Memory Disorder*
- 5. *History of prior lactulose use or HE within 6 months*
- 6. *Metastatic solid malignancy or blood malignancy*
- 7. *A1C > 12 (within past year)*
- 8. *Low galactose diet*

3.3 STUDY ENROLLMENT PROCEDURES

3.3.1 Identification and recruitment

After IRB approval, patients will be identified and recruited from multiple centers including Michigan Medicine. Patients will be identified by one of 6 methods: 1) referral by Michigan Medicine Hepatology providers, 2) screening of Michigan Medicine clinic schedules on the outpatient, transplant or procedure liver services, 3) referral from study coordinators of pre-existing registry studies at Michigan Medicine, 4) screening electronic medical records of Michigan Medicine hospitalized patients, 5) posting of study on www.UofMHealthResearch.org, 6) direct emails sent to cirrhosis patients via REDCap.

Patients with cirrhosis who have an email address are eligible to be contacted for recruitment by email via REDCap (see Appendix G). This will be conducted via a supplementary REDCap database in addition to the Mi-Kristal REDCap database. The supplementary REDCap database will be set to send a marketing email to new cirrhosis patients as they are added. The email will be shown as being sent from a group email: [contact]. Anyone interested can fill out an interest form via supplementary REDCap database and provide their contact information to the study team on this form. Once we receive the contact information, we will proceed to contact the patient via phone and proceed with enrollment and consent if they are interested. The study team will subsequently reach out to the patient by phone or email to complete the screening and enrollment process. Eligible patients at Michigan Medicine will be contacted by phone, email, or in-person to see if they are interested in participating in the study. To verify patient eligibility prior to enrollment, study staff will ask patients final screening questions as outlined in (see Appendix F).

3.3.2 Monitoring of recruitment targets

Data will be collected on all patients who are screened. A screening log will be maintained and will include the inclusion/exclusion criteria in Sections 3.1 and 3.2 above, and hence confirm eligibility or provide the reasons for ineligibility, as well as reasons for nonparticipation of eligible subjects. This will include: 1) the number of all persons screened with cirrhosis, 2) reasons for exclusion (specific criteria), 3) the number approached for participation, 4) the number enrolled, 6) the number who declined participation and 7) reasons for nonparticipation.

3.3.3 Consent Procedures

We will obtain written informed consent for participation from at least 50 subjects. A study coordinator will obtain informed consent. If recruitment procedures are being conducted in person, patients will be approached at the time of scheduled clinic appointments, procedures, or during hospitalizations. The study coordinator will obtain written informed consent during the in-person interaction. A copy of the informed consent form (ICF) will be provided to the subject.

If recruitment procedures are being conducted via email or phone, they will be consented electronically via SignNow, a third-party service to digitally collect informed consent which meets the requirements for HIPAA-compliance in the US. A copy of the informed consent form will be made available to the patient via email, or they can download a copy through SignNow.

4. STUDY INTERVENTIONS AND PROCEDURES

4.1 ASSESSMENTS

4.1.1 Baseline Assessments

1. Demographics Questionnaire (DQ) (Appendix A)

Participants will be asked to provide the following demographic information:

1. Sex
2. Age
3. Ethnicity
4. Race
5. Highest education level attained
6. Marital status
7. Occupation status
8. Income
9. Rural/Urban residence

2. Health History Questionnaire (HHQ) (Appendix B)

Participants will be asked to provide the following information:

1. Cause of cirrhosis
2. History of liver cancer
3. Liver transplant waitlist status
4. Driving status
5. Disability status (Katz-ADL)
6. Hospitalization within past 90 days
7. Emergency Room visit within past 90 days
8. Ascites status
9. Currently taking diuretics
10. Paracentesis within past 90 days
11. Hepatic encephalopathy status
12. Medications taken for HE
13. Dialysis status
14. Diabetes status
15. Congestive heart failure status
16. Chronic obstructive pulmonary disease status
17. Overall sleep quality (*PSQI*)
18. Falls in past 4 weeks
19. Average number of bowel movements per day

3. Short Form-8 Health Survey (SF-8) (Appendix C)

The SF-8 is an abbreviated version of an original 36-item health survey (SF-36). It is a generic multipurpose quality of life instrument. It contains psychometrically based physical and mental

health summary measures. The eight domains include general health, physical functioning, role physical, bodily pain, vitality, social functioning, mental health and role emotional.

4. Animal Naming Test (ANT) (Appendix D)

The animal naming test is a timed test that consists of subjects listing as many unique animals as possible in 60 seconds. This is a validated test used for the assessment of hepatic encephalopathy.

5. Alcohol Use Disorders Identification Test-C (AUDIT-C) (Appendix E)

The AUDIT-C is a brief 3-item alcohol screening instrument that reliably identifies persons who are hazardous drinkers or have active alcohol use disorders.

4.1.2 28-Day Follow-Up Assessments

1. Health Follow-Up Questionnaire (HFUQ) (Appendix G)

Participants will be asked to provide the following information:

1. Hospitalizations during study period
2. Overall sleep quality (PSQI)
3. Falls during study period
4. Average number of bowel movements per day
5. Ability to do regular daily activities (WPAI)

2. Short Form-8 Health Survey (SF-8) (Appendix C)

3. Animal Naming Test (ANT) (Appendix D)

4.2 ENROLLMENT PROCEDURES

4.2.1 Enrollment

After informed consent procedures, all subjects will complete enrollment procedures in the following order:

- a. Provide their contact information
- b. Randomization
- c. Baseline assessments
- d. Kristalose allocation and intervention counseling (*only if randomized to treatment group*)

In the control group, the date subjects are randomized and complete the baseline assessments is Study Day 1. These procedures can be conducted in person or via phone. In the treatment group, the date subjects receive Kristalose and receive intervention counseling is Study Day 1.

4.2.2 Randomization

After informed consent and baseline procedures are completed, the study coordinator will randomize the subject via reandomize.net. Subjects will be randomized in approximately equal allocation to each arm 1:1 lactulose therapy or the control group. Randomization is stratified by subject self-reported activity impairment level. Activity impairment level is determined by the baseline WPAI regular daily activity impairment score collected as part of the final screening questions (Appendix F): mild/moderate is a score of ≤ 7 , severe is a score of > 7 . To ensure approximate balance within arms, the randomization will be implemented using a randomly permuted blocks design to ensure approximate balanced assignments within subject self-reported

activity impairment severity level. The sequence of assignments for each stratum will be prepared in advance by a biostatistician.

4.2.3 Baseline Assessments

The study coordinator will conduct the following assessments with all subjects via phone, REDCap survey email or in person, after consent and randomization processes are complete:

1. Demographics Questionnaire
2. Health History Questionnaire
3. SF-8
4. ANT
5. AUDIT-C

4.3 INTERVENTION PROCEDURES

4.3.1 Lactulose Administration and Duration

Subjects randomized to the control are not required to complete any intervention activities or treatments. For subjects randomized to lactulose therapy, the following steps to implement the intervention will occur on Study Day 1:

1. The Principal Investigator (PI) will prescribe lactulose to subjects enrolled at Michigan Medicine. Lactulose (Kristalose) will be allocated to the patient in person at the University of Michigan through the Investigational Pharmacy. If enrollment procedures were conducted remotely, the patient will be allowed up to two weeks to schedule an appointment with the study coordinator to receive Kristalose.
2. Subjects will be instructed to take 20g of Kristalose (1 packet) in 4oz water twice daily for 28 days. All patients randomized to lactulose will receive standard counselling.
3. First, all subjects will be instructed to take the first dose on awakening and the second dose approximately 4 hours after the first dose.
4. Second, subjects will be asked to monitor their bowel movements (see section 4.3.2 Adherence Assessment below). If they achieve ≥ 4 bowel movements in one day outside of the adherence assessments, they will be asked to contact the study team directly and will be instructed to reduce their lactulose frequency to one 20g dose daily. No dose adjustments will be made to *increase* bowel movements. Study staff will be alerted via email if a subject reports more than 4 bowel movements per day. Subjects will be instructed to call the study phone line if their bowel movements do not decrease with a reduced dose. They will also be instructed to notify the study team if they are undergoing proctoscopy or colonoscopy and to avoid taking nonabsorbable antacids (like aluminum or magnesium hydroxide) with Kristalose since these may interfere with the lactulose activity.
5. Third, patients will be counselled on the side effects of lactulose including mild bloating, cramping or diarrhea. If the symptoms worry the patient, they will be instructed to reduce lactulose to one 10g dose on awakening and then to increase to 10g twice daily as tolerated.

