4.3.2 Adherence Assessment

During the 28-day intervention phase, all subjects will be contacted on Study Days 3, 6, 9, 14, 15, 21 and 28 via automated REDCap email or SMS text messages via Twilio service. Study Day 28 will only be collected via REDCap email or phone. These points of contact are to collect data about stool frequency and consistency among all subjects and therefore lactulose adherence in the treatment group. If the subject opts out of Twilio service, the subject can also receive these questions via REDCap automated email or a study coordinator will collect this data from the subject directly via phone or email. On Study Days 3, 6, 9, 14, 21 and 28 subjects will be asked the following questions:

1. "How many bowel movements did you have yesterday? Please respond with a whole number." *If 0-4 bowel movements are reported the subject will exit the survey. If >4, the subject will receive the following instructions:*

Since you had > 4 bowel movements yesterday, please reduce to **one** 20g dose of kristalose (1 packet) packet per day. Please call the study line at [contact] if you continue to have more than 4 bowel movements daily or with any questions or concerns.

On Study Day 15 subjects will be asked:

2. "Please reference the Bristol Stool Chart we provided to you to answer this question. How would you describe your stool looks today? Please respond with the applicable number, between 1-7. *All subjects exit survey after response.*

1. Separate hard lumps
2. Sausage-shaped but lumpy
3. Like a sausage but with cracks on its surface
4. Like a sausage or snake, smooth and soft
5. Soft blobs with clear cut edges
6. Fluffy pieces with ragged edges, a mushy stool
7. Watery, no solid pieces, entirely liquid

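### At exactly 4 stools a day, dose reduction depends on how the count is reported, and the automated dose message for more than 4 stools ignores arm and current dose

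*Combined protocol and SAP*

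**What the plan says.** **Self-monitoring (4.3.1, item 4).** This applies to subjects randomized to lactulose. The trigger reads "If they achieve ≥ 4 bowel movements in one day outside of the adherence assessments". Such a subject is to contact the team and go down to one 20 g dose daily. The same item adds "Study staff will be alerted via email if a subject reports more than 4 bowel movements per day" and "Subjects will be instructed to call the study phone line if their bowel movements do not decrease with a reduced dose".

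**Symptoms (4.3.1, item 5).** A subject worried by side effects is told to "reduce lactulose to one 10g dose on awakening and then to increase to 10g twice daily as tolerated".

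**Automated survey (4.3.2).** Here "all subjects will be contacted on Study Days 3, 6, 9, 14, 15, 21 and 28". Stool counts are asked on six of those days; Day 15 asks about stool form. The branch is "If 0-4 bowel movements are reported the subject will exit the survey". Above 4, the message opens "Since you had > 4 bowel movements yesterday, please reduce to" one 20 g packet per day, and gives the study line for use "if you continue to have more than 4 bowel movements daily or with any questions or concerns".

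**Recipients elsewhere.** The Summary limits these contacts to the treatment group, and section 7.4 describes the Twilio messages as going to the intervention groups. Section 2 states that controls receive neither drug nor placebo.

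**The concern.** These are dosing instructions that patients read and act on, some of them without staff involvement. Two things look wrong.

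First, the trigger for reducing the dose is not the same number throughout. Two treated subjects with the same count of 4 could be handled differently, one because they called and the other because they answered a text.

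Second, the automated message depends on the reported count alone. It assumes that the reader is on the full 40 g a day. Section 4.3.2 sends the survey to controls, who have no lactulose, and item 5 allows treated subjects to be on 10 g once daily, for whom one 20 g packet is more drug.

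At stake are consistent dosing in the lactulose arm, clear safety instructions and avoidable confusion among controls.

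**Working it through.** The plan states no figure to reproduce here. The check sets the rules side by side and works out the daily dose.

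**Step 1. Count the threshold statements.**

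| Place | Threshold |
|---|---|
| 4.3.1 item 4, self-monitoring | ≥4 |
| 4.3.1 item 4, staff alert | >4 |
| 4.3.2, survey branch | >4 |
| 4.3.2, message opening line | >4 |
| 4.3.2, message call-back line | >4 |

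Total: 1 at ≥4 and 4 at >4.

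**Step 2. Compare the action at each stool count (treated subject).**

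| Stools in a day | Self-monitoring | Survey and alert |
|---|---|---|
| 0–3 | none | none |
| 4 | contact team, reduce | exit survey, no alert |
| 5 or more | contact team, reduce | message to reduce, alert |

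The routes differ only at exactly 4.

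**Step 3. Apply the message to each regimen the protocol allows.** The message's target is 1 × 20 g = 20 g/day. The regimens come from 4.3.1, items 2, 4 and 5.

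| Current regimen | Before (g/day) | After (g/day) | Effect |
|---|---|---|---|
| 20 g twice daily | 2 × 20 = 40 | 20 | halved, as intended |
| 20 g once daily | 1 × 20 = 20 | 20 | none |
| 10 g twice daily | 2 × 10 = 20 | 20 | same daily total, in one dose |
| 10 g once daily | 1 × 10 = 10 | 20 | doubled, if followed literally |
| Control | 0 | not applicable | refers to a drug the subject does not have |

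Of the four treated regimens, one is lowered, two keep their daily total and one is given a higher target. That higher target of 20 g/day equals the most item 5 itself allows (10 g twice daily) and is 20/40 = 50% of the assigned dose.

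**Step 4. Who is contacted.** Section 4.3.2 says all subjects and gives its purpose as stool data in both arms. The Summary and section 7.4 point to the treated arm only. Exploratory Aim 5a compares episodes of more than 5 daily bowel movements between arms. The baseline and Day 28 questionnaires (Appendices B and G) ask only for an average per day, which cannot count episodes. The 4.3.2 reading is therefore the one that serves the aim.

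**The case against.** The case for leaving the text alone has real content.

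- **The threshold is a gap, not two opposing orders.** A reader might infer that the protocol tells a subject with 4 stools both to reduce and to stay on 40 g. It does not. The survey says nothing at 4, and leaving the survey does not cancel the counselling. A stricter trigger for an unsupervised message might even be deliberate, though the documents give no such reason. This stands, and it limits the point to one value.
- **The increase at 10 g needs a chain of events.** A reader might infer that the protocol doubles the dose in patients with diarrhoea. For that to happen, a subject must be on the first item 5 step, report more than 4 stools on a survey day, take 20 g although the message says to reduce, and not use the study line. Staff are also emailed at more than 4. An uncorrected increase is therefore unlikely. The count of one regimen in four is of regimens, not patients, and says nothing about frequency.
- **The control-arm part rests on 4.3.2.** The Summary and section 7.4 read differently, and the REDCap build may already branch by arm. The documents describe no such branch, and 4.3.2 is the operative section. For controls the result is confusion, not a dosing error.

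What remains is that the safeguards act after a faulty instruction has gone out, and that neither the alert nor the message reaches a survey answer of exactly 4.

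**Conclusion.** The point holds, and it is minor. The dose-reduction threshold is stated five times, once at ≥4 and four times at >4, which leaves a gap at exactly 4 that depends on the reporting route. The fixed message fits only one of the four permitted regimens: two get no reduction in daily dose and one is given a higher target. As 4.3.2 is written, controls can also receive it.

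This rests on reading 4.3.1 and 4.3.2 as the operative text and on there being no undescribed survey branch by arm or dose. The documents give no frequency of 4-stool days or of subjects on 10 g, so the effect on dose received cannot be estimated. A reader might go further and infer a bias in the trial's main result. The documents do not support that: nothing here enters the sample size, the power or the SF-8 analysis.

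**What to change.** 1. **One threshold in all five places.** The smallest edit is to change item 4 to >4. The sponsor may instead choose ≥4 throughout, but must then also change the message's opening line, or a subject reporting 4 would be told they had more than 4. That choice brings more alerts and dose reductions, whose number the documents do not allow to be estimated.
2. **Send the dose text to treated subjects only**, worded so that it cannot raise a dose: *if you take more than one 20 g packet a day, reduce to one; otherwise call the study line.*
3. **Correct the Summary and section 7.4** to say that all subjects are contacted, to match 4.3.2 and the between-arm comparison in Aim 5a.

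The cost is a written amendment with IRB approval before implementation (section 8.4), revised survey text and one survey branch on arm. No extra visits, patients or drug are needed.

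### The automated message for more than 4 bowel movements names a fixed 20g/day and does not fit a subject already stepped down to 10g once daily

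*Combined protocol and SAP*

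**What the plan says.** Section 4.3.1 starts treated subjects on one 20g packet twice daily and gives two ways down.

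- **Step 4, stool frequency.** Subjects who reach the step's stool threshold outside the scheduled contacts are to get in touch with the study team and "will be instructed to reduce their lactulose frequency to one 20g dose daily". The same step adds a safeguard: "Study staff will be alerted via email if a subject reports more than 4 bowel movements per day". It also rules out raising the dose to produce more bowel movements.
- **Step 5, side effects.** Subjects are counselled about bloating, cramping and diarrhea. If symptoms worry them, "they will be instructed to reduce lactulose to one 10g dose on awakening and then to increase to 10g twice daily as tolerated".

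Section 4.3.2 sets the automated contacts: "On Study Days 3, 6, 9, 14, 21 and 28 subjects will be asked the following questions". The question asks only how many bowel movements occurred the day before. A count of 0 to 4 ends the survey. Otherwise: "If >4, the subject will receive the following instructions". The text opens with "Since you had > 4 bowel movements yesterday, please reduce to" and then gives the target as one "20g dose of kristalose (1 packet) packet per day". It closes by asking the subject to ring the study line "if you continue to have more than 4 bowel movements daily or with any questions or concerns".

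Section 4.3.3 says that the pharmacy dispenses 20g packets, so a 10g dose is half a packet.

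**The concern.** Step 5 creates a permitted dose of 10g once daily and sets no time limit on it, so it can coincide with a scheduled contact. The message does not recognise that dose. The survey does not ask what the subject is taking, and the only branch is on the stool count.

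Diarrhea is one of the side effects listed in step 5, so a subject on 10g once daily could plausibly report more than 4 bowel movements and receive the message. Step 5 allows a rise from 10g only if it is tolerated, and more than 4 bowel movements a day suggests poor tolerance. Yet the one dose figure the subject then receives is higher than the current dose. Section 8.3 lists diarrhea among the risks of lactulose, with dehydration and electrolyte disturbance as rare ones.

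What is at stake is the dose taken by a symptomatic subject. The estimate of treatment effect is not in question.

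**Working it through.** The documents give no figure to reproduce here. The check compares the daily total named in the message with each daily total that the protocol permits.

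**Inputs**
- Assigned dose: 20g twice daily, so 2 × 20 = 40g/day (4.3.1, step 2).
- After the step 4 reduction: 20g once daily = 20g/day.
- Step 5, first level: 10g once daily = 10g/day.
- Step 5, second level: 10g twice daily, so 2 × 10 = 20g/day.
- Dose named in the message: one 20g packet = 20g/day (4.3.2).

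**Formula:** ratio = message dose / current dose; difference = message dose − current dose.

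| Current regimen | Current total | Ratio | Difference |
|---|---|---|---|
| 20g twice daily | 40g/day | 20/40 = 0.5 | −20g/day |
| 20g once daily | 20g/day | 20/20 = 1.0 | 0 |
| 10g twice daily | 20g/day | 20/20 = 1.0 | 0 |
| 10g once daily | 10g/day | 20/10 = 2.0 | +10g/day |

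The message works as intended in the first row and leaves the total unchanged in the next two. Only in the last row is the named dose above the current one, by 10g/day or 100%. Even then 20g/day is half of the assigned 40g/day.

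**When it can arise.** The bowel-movement question is asked on Days 3, 6, 9, 14, 21 and 28. Day 28 is the last treatment day, so the message can affect later dosing at 6 − 1 = 5 contacts.

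**Whether other text settles it.** Three places could supply a rule for the 10g subject:
1. The survey does not record current dose, so the message cannot be tailored.
2. The staff alert in step 4 is tied to the same trigger, but no dose check or correction is specified to follow it.
3. The closing line of the message covers continued symptoms, questions and concerns. A 10g subject who is puzzled has a number to ring, but nothing tells that subject to stay on 10g meanwhile.

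No section says what a subject on 10g once daily should do on receiving the message.

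**The case against.** The strongest reply is that the message does not order an increase. Its verb is *reduce*, and nobody can reduce from 10g to 20g. A sensible subject would see that the text does not apply, or would take one packet as an upper limit. This stands in part. A reader might infer that the protocol tells these subjects to double their dose, but the text does not plainly say so. It fails to fit them. It does still name a specific dose, one packet, and nothing says that this is a ceiling.

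A second reply is that safeguards already act on the same trigger. This also stands: staff are emailed, and every recipient, including the 10g subject, is given the study line. These limit the harm, but the unsuitable text reaches the subject before either takes effect.

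Third, a reader might say that step 4 has the same defect because it also names 20g. Its problem is milder. It speaks of cutting *frequency*, which a once-daily subject cannot do, and it runs through direct contact with the study team, who can ask the current dose.

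Fourth, a reader might bound the excess by the gap to the next bowel-movement question. The gaps run from 6 − 3 = 3 to 28 − 21 = 7 days, which suggests 10 × 3 = 30g to 10 × 7 = 70g. The documents do not support that range. The next contact corrects nothing: a count of 0 to 4 ends the survey and a higher count repeats the same 20g text, so the excess could last longer. In the other direction, step 5 may itself bring the subject to 10g twice daily, which is also 20g/day, and then the excess shrinks or disappears.

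Finally, the exposed group is small. The subject must be one of about 25 treated (section 2), have stepped down for side effects, still be at the first level, report more than 4 bowel movements at one of five contacts, and then read a reduction as an increase.

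**Conclusion.** The gap is real and minor. The section 4.3.2 message names 20g/day whatever the current dose, and so does not fit the 10g-once-daily regimen that section 4.3.1, step 5 permits. Read literally, it names twice that subject's dose (+10g/day), when bowel movements are excessive and without step 5's tolerance condition.

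The textual gap is certain. A dosing consequence is not: it needs a subject still on 10g once daily at a contact day who takes the message literally before a call or staff action corrects it. The documents do not show how often that would happen, and it may never happen. No cumulative excess can be stated.

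A reader might also infer a threat to the trial's main result. Nothing here supports that: the SF-8 comparison, sample size, power and error rate do not depend on this message.

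**What to change.** Leave the step 5 dosing as it is. In section 4.3.2, replace the dose sentence of the message with: *If you take 2 packets a day, reduce to 1 packet a day. If you already take 1 packet a day or less, do not increase your dose; call the study line.* This keeps the intended halving for subjects on 40g/day and sends every lower dose to a person who can ask about it.

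For consistency, state in section 4.3.1, step 4 that the reduction to one 20g dose daily applies only to subjects taking more than 20g/day.

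The cost is one edited automated text and one added sentence, submitted as an amendment under section 8.4, and perhaps a few more calls to the study line. Drug supply, contact schedule, sample size and analysis do not change.
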